## 6 STUDY PROCEDURES

### 6.1 SCHEDULE OF STUDY PROCEDURES

A schedule of events is presented in [Table 3](#). Laboratory tests, including PD assays, are specified in [Appendix A](#).

Table 3 - Study schedule of events

Study Visit (Week/Day)	Screening/ Observation Period a	Baseline	Part A Dosing (Weeks 1–25)	Part A EOT: Part B Crossover Loading Dose (Week 26)	Part B Open- Label Extension Phase	ET/EOS/ Safety Follow- up b
	Days -42 to -1	Day 0	Days 7, 21, 35, 49, 63, 77, 91, 105, 119, 133, 147, 161, 175	Day 182	Every 2 Weeks after Week 25	9 Weeks after Last Dose
Visit Windows	± 3 days	N/A	± 2 days	± 2 days	± 2 days	± 2 days
Written informed consent	X					
Demographic & baseline characteristics	X					
Detailed medical history	X					
Inclusion/exclusion criteria	X	X				
Immunization review/vaccination c	When applicable, vaccinations should be initiated on Day -42 or as soon as possible during Screening. The primary vaccine series should be completed during Screening when possible and otherwise prior to Week 5 of Part A. See Appendix I for the vaccination schedule for Japan.					
Bone marrow biopsy report review d	X					
Optional bone marrow testing for MYD88 status for consenting patients	X					
Pregnancy test (if applicable) e	X	X	X (Prior to study drug infusion on Days 21, 49, 77, 105, 133, and 161) e	X	X e	X
Body weight and height f	X	X		X	X l	X
Physical examination, full	X			X		X
Physical examination, brief		X	X		X l	

Study Visit (Week/Day)	Screening/ Observation Period a	Baseline	Part A Dosing (Weeks 1–25)	Part A EOT: Part B Crossover Loading Dose (Week 26)	Part B Open- Label Extension Phase	ET/EOS/ Safety Follow- up b
	Days -42 to -1	Day 0	Days 7, 21, 35, 49, 63, 77, 91, 105, 119, 133, 147, 161, 175	Day 182	Every 2 Weeks after Week 25	9 Weeks after Last Dose
Visit Windows	± 3 days	N/A	± 2 days	± 2 days	± 2 days	± 2 days
Vital signs (BP, PR, RR, body temperature) g	X	X	X	X	X l	X
12-lead electrocardiogram (predose and 1 hour after infusion on dosing days)	X	X	X (Day 91 only)		X p	
Virology/serology panel h	X					
Gilbert's Syndrome test (UGT1A1 gene)	X					
SLE panel h	X			X	X t	X
Iron panel and erythropoietin h	X					
Hematology panel h	X	X	X	X	X	X
Coagulation panel h	X	X		X		X
Clinical chemistry panel h	X	X	X	X	X	X
Urinalysis h	X	X		X	X l	X
FACIT-Fatigue r		X	X	X	X l	X
PGIS r		X	X (Days 35, 77, and 119 only)	X	X l	X
PGIC r		X	X (Days 35, 77, and 119 only)	X	X l	X
SF-12 r		X	X (Days 35, 77, and 119 only)	X	X l	X
EQ-5D-5L r		X	X (Days 49, 91, 133 only)	X	X l	X

Study Visit (Week/Day)	Screening/ Observation Period a	Baseline	Part A Dosing (Weeks 1–25)	Part A EOT: Part B Crossover Loading Dose (Week 26)	Part B Open- Label Extension Phase	ET/EOS/ Safety Follow- up b
	Days -42 to -1	Day 0	Days 7, 21, 35, 49, 63, 77, 91, 105, 119, 133, 147, 161, 175	Day 182	Every 2 Weeks after Week 25	9 Weeks after Last Dose
Visit Windows	± 3 days	N/A	± 2 days	± 2 days	± 2 days	± 2 days
Solicited symptomatic anemia	X (Day -42 only)	X	X	X	X	X
Study drug administration i		X	X	X m	X	
ADAs against BIVV009		X	X s	X s	X s	X
PK Samples j		X	X	X	X l	X
PD Samples h, j	X n	X	X	X	X l	X
Disease-related biomarkers h	X	X	X o (Day 91 only)	X		
Prior & concomitant medications including transfusions	X	X	X	X	X	X
Healthcare resource utilization	X	X	X (Days 21, 49, 77, 105, 133, and 161)	X	X q	X
Adverse events k	X	X	X	X	X	X

ADA = anti-drug antibodies; BP = blood pressure; EOS = End of Study; EOT = End of Treatment; EQ-5D-5L = five level EuroQol five dimensions questionnaire; ET = Early Termination Visit; FACIT-Fatigue = functional assessment of chronic illness therapy - fatigue; N/A = not applicable; PD = pharmacodynamic; PGIC = Patient's Global Impression of Change; PGIS = Patient's Global Impression of [Fatigue] Severity; PK = pharmacokinetic; PR = pulse rate; QOL = quality of life; RR = respiratory rate; SF-12 = 12-Item Short Form Survey; SLE = systemic lupus erythematosus.

a The 6-week Screening/Observation Period may be extended by 1 week for patients requiring a blood transfusion during Screening/Observation prior to study drug administration.

b Patients should return to site 9 weeks after last dose for ET procedures, EOS assessment, or Safety Follow-up procedures upon completion of dosing in the study. If patient experiences a hematological breakthrough event, a PK, PD, and ADA sample should be collected at the time of the event.

c Applicable to patients who do not have documented vaccination against encapsulated bacterial pathogens within 5 years of enrollment. Refer to immunization recommendations per Section 6.1.1.1 for patients requiring vaccination. A blood sample for vaccine titers will be collected on Day 0 prior to study drug infusion to be used to determine serum relevant antibody titers should the patient be diagnosed with an infection associated with an encapsulated organism during the study. A second sample will be collected during the study period if a patient presents with symptoms of infection.

- d* Prior bone marrow biopsy report review, prior tissue assessment, or new bone marrow biopsy (as applicable). Sites will submit de-identified biopsy reports to independent central reader for eligibility adjudication. If biopsy is deemed unsuitable or insufficient to determine eligibility, either prior tissue may be submitted for additional hematopathology assessment or a new bone marrow biopsy will be performed during the screening period.
- e* Females of child-bearing potential only. Serum pregnancy test to be performed at Screening. Serum or urine pregnancy test in WOCBP (ie, women of child bearing potential) to be performed on Days 0, 21, 49, 77, 105, 133, and 161, and at Week 26/EOT or at the ET visit. Repeat serum or urine pregnancy test every 4 weeks ( $\pm 2$  days) during Part B.
- f* Height measured at Screening only. Body weight measured every 3 months during Part B.
- g* Vital signs measurements (supine BP, PR, RR, and oral temperature) are to be obtained at Screening and at each subsequent visit, with measurements performed predose and 1 hour ( $\pm 5$  minutes) after completion of administration of each dose of study drug.
- h* For a complete list of analytes, see protocol [Appendix A](#).
- i* Study drug doses of 6.5 grams (if  $< 75$  kg) or 7.5 grams (if  $\geq 75$  kg) based on patient's baseline body weight will be administered via IV infusion over  $\sim 60 \pm 5$  minutes on Days 0, 7, and every 14 days thereafter during Part A and every 2 weeks starting at Week 27 during Part B. Patients with underlying cardiopulmonary disease may receive a 2-hour infusion with Sponsor approval. If a patient misses a scheduled dose (outside of the 2-day window or  $> 17$  days since last dose), they must return to site (unscheduled visit) to receive another loading dose 1 week prior to the next scheduled dose. Qualifying patients at participating sites may have study drug dosed at home during certain visits in Part B, according to the rules specified in Appendix K (for the US, the Netherlands, Norway, France, Italy, Austria, Germany, and Spain specific amendments ([Appendix K](#))).
- j* During Part A, PK and PD blood samples will be collected at predose and 1 hour ( $\pm 15$  minutes) post-dose (ie, 1 hour after completion of study drug infusion) from all patients on Days 0, 7, 21, 35, 49, 63, 77, 91, 105, 119, 133, 147, 161, and 175. An additional blood sample for PK and PD analysis will be collected during the EOT visit on Day 182 or at ET if a patient withdraws early. During Part B, PK and PD samples will continue to be collected at predose and 1 hour ( $\pm 15$  minutes) postdose on Days 189, 217, and 245, then routinely at 3-month intervals starting at Day 273 through the remainder of the study. PK and PD samples will also be collected if a patient experiences a hematologic breakthrough event at any point during the study.
- k* AEs will be recorded from the time the patient signs the informed consent form until 9 weeks after administration of the last dose of study drug.
- l* To be performed every 3 months during the on-site visits, or for post-infusion vital signs in case of undiluted administration, after each undiluted infusion.
- m* After completion of all Part A EOT assessments, a cross-over loading dose will be administered to patients in a blinded manner at the Week 26 visit to initiate dosing in Part B.
- n* Refer to the Laboratory Manual for details of sample collection during Screening.
- o* Samples will be collected for a subset of the disease-related biomarkers at Day 91. Refer to the Laboratory Manual for details.
- p* During Part B, a 12-lead ECG will be conducting pre- and postdose at 3 months (Day 273).
- q* During Part B, the healthcare resource utilization data will be recorded every 4 weeks.
- r* To be performed in the following order: FACIT-Fatigue first, PGIS second, PGIC third, SF-12 fourth, and EQ-5D-5L fifth.
- s* During Part A, ADA samples will be collected at predose on Day 0, Day 7, 35, 77, 133, 175 and on Day 182 (EOT) or at ET if a patient withdraws early. During Part B, ADA samples will continue to be collected at predose, on Days 189, 217, and 245, then routinely at 3-month intervals starting at Day 273 through the remainder of the study and at safety follow up visit 9 weeks after last dose. Samples will also be collected if a patient experiences a hematologic breakthrough event or withdraws from the study early.
- t* SLE panel will be performed every 6 months in Part-B of the study.

### **6.1.1 Screening/observation period (Days -42 to Day -1)**

Patients (or their legally authorized representative) must provide informed consent before any study-specific screening tests are performed. Participating study sites are required to document all screened candidates initially considered for inclusion in the study. Patients will be designated as screened following completion of all screening assessments.

Screen failures are defined as patients who sign the informed consent form (ICF) but are not subsequently dosed with BIVV009 or placebo. If a patient is considered a screen failure, the reason(s) will be documented on the screening log and in source records.

A minimal set of screen failure information is required to ensure transparent reporting of screen failure participants to meet the Consolidated Standards of Reporting Trials publishing requirements and to respond to queries from regulatory authorities. Minimal information includes demography, screen failure details, eligibility criteria, and any SAEs.

#### **6.1.1.1 Screening assessments (initiating at Day -42)**

The following assessments and procedures will be initiated following collection of written informed consent at Day -42 and completed during the 6-week Screening/Observation Period:

- Written informed consent
- Demographic and baseline characteristics including height and body weight
- Detailed medical history
- Immunization review and vaccination, if applicable
- Serum pregnancy test (if applicable)
- Physical examination (full)
- Vital signs
- Virology/serology panel
- Gilbert's Syndrome testing (UGT1A1 gene)
- SLE panel
- Hematology panel
- Coagulation panel
- Clinical chemistry panel
- Urinalysis
- PD samples (refer to Laboratory Manual)
- Iron panel and erythropoietin assays
- Disease-related biomarkers

- 12-lead ECG
- Prior bone marrow biopsy report review, prior tissue assessment, or new bone marrow biopsy (as applicable)
- Optional bone marrow testing for MYD88 status
- Inclusion/exclusion criteria review for determination of eligibility
- Solicited symptomatic anemia assessment
- Record healthcare resource utilization data from previous 6 months
- Record prior and concomitant medications/procedures including transfusions
- Adverse event monitoring

### **Bone Marrow Biopsy**

A bone marrow biopsy is required to have been performed within 6 months of Screening to rule out overt evidence of lymphoproliferative disease or other hematological malignancy prior to enrollment. Sites will submit de-identified biopsy reports to an independent central reader for eligibility adjudication. If biopsy is deemed unsuitable or insufficient to determine eligibility, then either the prior tissue may be submitted for additional hematopathology assessment or a new bone marrow biopsy will be performed during the screening period. Patients will have the option to consent to additional testing of bone marrow for MYD88 status. Further instructions for bone marrow biopsy assessment will be available in [Appendix A](#) (Bone Marrow Biopsy Report Review Process) to the ‘Subject Eligibility Review Process Overview’.

### **Vaccination Against Encapsulated Bacterial Pathogens**

In the event a patient does not have documented vaccination against encapsulated bacterial pathogens (*Neisseria meningitidis*, including serogroup B *meningococcus*, where available, *Haemophilus influenzae*, and *Streptococcus pneumoniae*) within 5 years prior to enrollment, vaccination should be initiated during the Screening/Observation Period prior to enrollment (see [Table 3](#)). Vaccination series for these pathogens should be completed as per current regional guidelines specified for patients with persistent complement deficiency and in accordance with their respective labels, as applicable. Where no regional guidelines are available for patients with persistent complement deficiency, it is recommended that vaccinations include meningococcal conjugate, meningococcal serogroup B, 13-valent pneumococcal, 23-valent pneumococcal, and *Haemophilus influenzae* Type b vaccines where commercially available.

Vaccinations should be initiated on Day -42 or as early as possible during the Screening/Observation period. The primary vaccine series should be completed during Screening when possible and otherwise prior to Week 5 of Part A. Patients must be advised that vaccination may not prevent meningococcal infections and that they should immediately report fevers or other symptoms consistent with acute infection to the Investigator.

Patients who develop symptoms consistent with an infection due to encapsulated bacterial pathogens during the study period will have a blood sample collected to test for confirmation of infection and vaccination status.

A separate vaccination schedule for Japan is provided in [Appendix I](#).

## Laboratory Tests

The first set of laboratory test results collected during the Screening Period will be utilized to assess patient eligibility for the study. Screening assessments may be repeated once at the discretion of the Principal Investigator (PI). Additional repeat screening tests may not be performed without Sponsor (or designee) approval.

### **6.1.1.2 Interim visits during screening/observation period**

During the 6-week Screening/Observation Period, the patient will return to the clinical site approximately every 2 weeks (Day -28 and Day -14) after the initial visit for collection of laboratory samples to assess and characterize their CAgD. During these visits, the following assessments and procedures will be performed:

- Vital signs
- Collection of blood samples for assessment of the following indicators of CAgD:
  - Hemoglobin
  - Bilirubin
  - LDH
  - Haptoglobin
  - Reticulocytes
  - CH50
- Record prior and concomitant medications/procedures including transfusions
- Adverse event monitoring

Detailed information on sample collection and a list of analytes to be tested may be found in the Study Schedule of Events ([Table 3](#)) in [Section 6.1](#), [Appendix A](#), and the Laboratory Manual.

### **6.1.1.3 Confirmatory review of patient eligibility**

Upon completion of screening assessments, the site will compile de-identified, key eligibility data for each patient and forward to the Study Medical Monitor for review and confirmation of eligibility prior to study enrollment/randomization. Details on the eligibility data review process may be found in the ‘Subject Eligibility Process Overview’.

### **6.1.2 Day 0 visit (first dose)**

On Day 0, patients will undergo the following procedures before administration of the study drug:

- Inclusion/exclusion criteria review for confirmation of continued eligibility
- Serum or urine pregnancy test (if applicable)

- Vaccine titers
- Body weight
- Physical examination (brief)
- Vital signs
- Hematology panel
- Coagulation panel
- Clinical chemistry panel
- Urinalysis
- Solicited symptomatic anemia assessment
- QOL assessments
  - FACIT-Fatigue ([Appendix C](#))
  - EQ-5D-5L ([Appendix D](#))
  - SF-12 ([Appendix E](#))
  - PGIS (see [Appendix H](#))
  - PGIC (see [Appendix F](#))
- ADAs against BIVV009
- PK and PD sampling
- Disease-related biomarkers
- Record healthcare resource utilization data (see [Appendix G](#)) since previous assessment
- 12-lead ECG
- Record prior and concomitant medications/procedures including transfusions
- Adverse event monitoring

At 0 hour, study drug will be infused via an indwelling IV catheter over a period of 60±5 minutes. Patients with underlying cardiopulmonary disease may receive a 2-hour infusion with Sponsor approval. Additionally, study drug infusion may be interrupted or slowed in the event of suspicion of an allergic reaction or anaphylaxis.

After completion of the infusion, patients will undergo the following procedures:

- Vital signs at 1 hour (±5 minutes) postdose
- 12-lead ECG at 1 hour (±15 minutes) postdose
- PK and PD sampling at 1 hour (±15 minutes) postdose

### 6.1.3 Weeks 1-25 Part-A

On Days 7, 21, 35, 49, 63, 77, 91, 105, 119, 133, 147, 161, and 175, patients will undergo the following procedures before administration of the study drug:

- Serum or urine pregnancy test in WOCBP (ie, women of child bearing potential), if applicable, on Days 21, 49, 77, 105, 133, and 161
- Physical examination (brief)
- Vital signs
- Hematology panel
- Clinical chemistry panel
- Solicited symptomatic anemia assessment
- QOL assessments:
  - FACIT-Fatigue: all scheduled visits
  - PGIS: Days 35, 77, and 119 only
  - PGIC: Days 35, 77, and 119 only
  - SF-12: Days 35, 77, and 119 only
  - EQ-5D-5L: Days 49, 91, and 133 only
- 12-lead ECG (Day 91 only)
- During Part A, ADA samples will be collected at predose on Day 0, 7, 35, 77, 133, 175 on Day 182 (EOT)
- PK and PD sampling
- Disease-related biomarkers (subset at Day 91 only); refer to the Laboratory Manual for details
- Record healthcare resource utilization data since previous assessment on Days 21, 49, 77, 105, 133, and 161
- Record concomitant medications/procedures including transfusions
- Adverse event monitoring

At 0 hour, study drug will be infused via an indwelling IV catheter over a period of 60 ±5 minutes. Patients with underlying cardiopulmonary disease may receive a 2-hour infusion with Sponsor approval. Additionally, study drug infusion may be interrupted or slowed in the event of suspicion of an allergic reaction or anaphylaxis.

After completion of the infusion, patients will undergo the following procedures:

- Vital signs at 1 hour (±5 minutes) postdose
- 12-lead ECG (Day 91 only) at 1 hour (±15 minutes) postdose
- PK and PD sampling at 1 hour (±15 minutes) postdose

Vaccinations should be administered according to [Section 6.1.1.1](#), if applicable, or [Appendix I](#) for Japan.

Note: Patients who miss a dose (ie, outside the dosing window or >17 days since last dose) should return to the site for an unscheduled visit 1 week prior to the next scheduled dose in order to receive an additional loading dose. The patient should then resume subsequent dosing visits every 14 days after the loading dose.

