
Methodology/Study Design:
	
This randomized, double-blind, placebo-controlled study is designed to evaluate the efficacy, safety, and tolerability of BIVV009 in symptomatic patients with the complement-mediated disorder primary CAgD who do not have a recent history of blood transfusion.
 
During the 6-week Screening/Observation Period, prospective patients will have a detailed medical history documented (including all available transfusion history), physical evaluations, and blood samples collected for characterization of CAgD biomarkers, including Hgb levels on 3 occasions approximately every 2 weeks.
 
Patients under screening for Cadenza who require a transfusion(s) during the Screening/Observation Period prior to the first study drug infusion (if medically indicated per the Investigator's discretion and within the parameters of the protocol specified transfusion criteria, see Table 1) will remain eligible. If a patient receives a transfusion(s) during the Screening/Observation Period prior to the first study drug infusion, the baseline visit (and first infusion of study drug) must occur at least 7 days following the transfusion.
 
Part A
 
The study will enroll approximately 40 primary CAgD patients who do not have a recent history of blood transfusion (ie, <math>\leq 1</math> transfusion during the last year and no transfusion during the last 6 months prior to enrollment). Eligible patients should have been diagnosed with primary CAgD at least 6 months prior to enrollment and should have had no history of transfusion during this period.
 
Eligible patients will be randomized 1:1 to receive an intravenous (IV) infusion of BIVV009 or placebo over approximately 60 minutes on Day 0, Day 7, and every 14 days thereafter through Week 25 (ie, Days 21, 35, 49, 63, 77, 91, 105, 119, 133, 147, 161, and 175). Patients who miss a dose (ie, outside the dosing window or <math>>17</math> days since last dose) should return to the site for an unscheduled visit to receive another loading dose prior to their next scheduled visit. Patients will have an End-of-Treatment (EOT) visit in Part A on Day 182 (Week 26).
 
Patients who meet the transfusion criteria in Table 1 during the 6-month double-blind treatment period will receive a transfusion. Patients who receive a transfusion during Part A will not be withdrawn from the study and will be eligible to participate in Part B.
 
Table 1: Transfusion criteria
 
 
A patient will receive a transfusion during Part A or Part B if his or her Hgb level meets either of the following criteria:
 
 
• Hgb is <math><9</math> g/dL and the patient is symptomatic, or
 
• Hgb is <math><7</math> g/dL and the patient is asymptomatic
 
 
 
A responder analysis will be conducted following completion of the EOT visit at Week 26. The responder definition is provided in Table 2.
 
Table 2: Responder definition
 
 
A patient will be considered a responder in Part A if:
 
 
• Hgb increases <math>\geq 1.5</math> g/dL from baseline (defined as the last Hgb value before administration of the first dose of study drug) at treatment assessment endpoint (defined as mean value from Weeks 23, 25, and 26) and
 
• The patient did not receive a blood transfusion from Week 5 through Week 26 (EOT), and
 
• The patient did not receive treatment for CAgD beyond what is permitted per protocol from Week 5 through Week 26 (EOT)
 
 

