### 2.2.3 Pharmacokinetic experience and dose justification

The pharmacokinetic/pharmacodynamic (PK/PD) profile of BIVV009 in healthy volunteers and in patients has been established based on the data collected from the first-in-human clinical trial. A human PK model was constructed from the complete and final Phase 1a data. This model was then augmented with the available PK data emerging from the Phase 1b component of this trial, and the combined model was used to simulate a variety of possible dose regimens for use in patients. The dose regimen proposed for use in current and future clinical trials with BIVV009, including Study BIVV009-04, differs from that used in the Phase 1a and 1b program because weekly IV administration was deemed to be logistically challenging for patients when the period of treatment is increased from weeks to months. A regimen based upon a single priming dose on Day 0, followed by bi-weekly dosing on Days 7, 21, 35, 49, etc, can provide continuous, complete C1s inhibition while better accommodating to the needs of patients. Human PK modeling suggests that a dose level of 6.5 grams or 7.5 grams (based on body weight of <75 kg or  $\geq 75$  kg, respectively) is necessary to protect patients better from potential restoration of CP activity at the end of the inter-dose interval. The weight cut-off of 75 kg was chosen based on the expected weight distribution in CAgD patients with a median weight of 74.8 kg.

The in vitro and in vivo pharmacologic profile of BIVV009 has two especially important features that help to define the optimal dose regimen for clinical use. First, BIVV009 has very high affinity and selectivity for C1s, with negligible off-target activity. Second, it is a potent CP inhibitor with such a steep concentration-effect relationship that it behaves as a switch-like inhibitor of C1s: at concentrations of BIVV009  $\geq 20$   $\mu\text{g/mL}$ , CP activity is virtually undetectable; at BIVV009 concentrations below this threshold the CP is fully active. This property results in the requirement to maintain a blood concentration of BIVV009 that is always at least  $\geq 20$   $\mu\text{g/mL}$ , even at trough, lest CP activity be fully restored.

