#### Part A

The study will enroll approximately 40 primary CAgD patients who do not have a recent history of blood transfusion (ie,  $\leq 1$  transfusion during the last year and no transfusion during the last 6 months prior to enrollment). Eligible patients should have been diagnosed with primary CAgD at least 6 months prior to enrollment and should have had no history of transfusion during this period.

Eligible patients will be randomized 1:1 to receive an IV infusion of BIVV009 or placebo over approximately 60 minutes on Day 0, Day 7, and every 14 days thereafter through Week 25 (ie, Days 21, 35, 49, 63, 77, 91, 105, 119, 133, 147, 161, and 175). Patients who miss a dose (ie, outside the dosing window or  $>17$  days since last dose) should return to the site for an unscheduled visit 1 week prior to the next scheduled dose in order to receive an additional loading dose. Patients will have an End-of-Treatment (EOT) visit in Part A on Day 182 (Week 26).

Patients who meet the transfusion criteria in [Table 1](#) during the 6-month double-blind treatment period will receive a transfusion. Patients who receive a transfusion during Part A will not be withdrawn from the study and will be eligible to participate in Part B.

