## 4.4 DURATION OF THE STUDY

The planned total study duration per patient is approximately 1.5 to 2.5 years:

- Screening/Observation Period: 6 weeks (Day -42 through Day -1)
- Part A treatment period: 25 weeks (Day 0 through Day 175)
- Part A EOT visit: 1 week after administration of the last dose of study drug during Part A (Week 26/Day 182)

Patients who complete Part A per protocol through the EOT visit will participate in Part B, the long-term safety and durability of response extension phase of the study.

- Part B safety and durability of response extension phase: blinding will be maintained when rolling patients into the extension period by providing a crossover dose at Week 26 to allow placebo patients to receive the BIVV009 loading dose at start of BIVV009 dosing. Patients who were randomized to BIVV009 during the 6-month treatment period will receive a placebo dose at Week 26 to maintain blinding. All patients will then continue to receive bi-weekly BIVV009 dosing starting at Week 27. For individual patients, dosing in Part B may last from 1 to 2 years, depending on when the patient enters Part B. Part B will run for 1 year following completion of LPO in Part A.
- Part A/B ET/Safety Follow-up visit: 9 weeks after administration of the last dose of study drug.

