1 INTRODUCTION

1.1 STUDY DESIGN

This is a randomized, double-blind, placebo-controlled, multicenter study designed to evaluate the efficacy and safety of BIVV009 in symptomatic patients with the complement-mediated disorder, primary CAD, who do not have a recent history of blood transfusion.

During the 6-week Screening/Observation Period, prospective patients will have a detailed medical history documented (including all available transfusion history), physical evaluations, and blood samples collected on 3 occasions approximately every 2 weeks.

The study will enroll approximately 40 primary CAD patients who do not have a recent history of blood transfusion (ie, ≤ 1 transfusion during the last year and no transfusion during the last 6 months prior to enrollment). Eligible patients should have been diagnosed with primary CAD at least 6 months prior to enrollment and should have had no history of transfusion during this period.

Eligible patients are randomized with a ratio of 1:1 to BIVV009 or Placebo by a permuted block randomization. The block size is fixed at 4. The randomization is performed by Pharm-Olam's Interactive Web Response System (IWRS). Sponsor personnel (except for those who provide drug supply) are blinded to the treatment assignment until the interim analysis (defined below).

Eligible patients will be randomized 1:1 to receive an IV infusion of BIVV009 or placebo over approximately 60 minutes on Day 0, Day 7, and every 14 days thereafter through Week 25 (ie, Days 21, 35, 49, 63, 77, 91, 105, 119, 133, 147, 161, and 175). Patients who weigh less than 75 kg will receive fixed doses of 6.5 g of BIVV009 or placebo. Patients who weigh 75 kg or more will receive fixed doses of 7.5 g of BIVV009 or placebo. Patients who miss a dose (ie, outside the dosing window or >17 days since last dose) should return to the site for an unscheduled visit 1 week prior to the next scheduled dose in order to receive an additional loading dose. Patients will have an EOT visit on Day 182 (Week 26).

During the 6-month treatment period, patients will receive a transfusion, if his or her Hgb level meets either of the following criteria:

- Hgb is <9 g/dL and the patient is symptomatic, or
- Hgb is <7 g/dL and the patient is asymptomatic.

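### Protocol 6.1.3 restarts dosing 14 days after a repeat loading dose, against the 1-week rule stated everywhere else; after one missed dose (Day 7 to Day 161) this gives 13 of 14 Part A doses, the last on Day 168

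*Protocol*

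**What the plan says.** Part A dosing is on Day 0, Day 7 and every 14 days thereafter to Day 175. A dose counts as missed when it falls "ie, outside the dosing window or >17 days since last dose" (Protocol 6.1.3). The patient then returns for an extra loading dose.

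The timing of that dose is stated consistently:

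- Protocol 4.1, Part A: the patient "should return to the site for an unscheduled visit 1 week prior to the next scheduled dose".
- Protocol Table 3, footnote i: "they must return to site (unscheduled visit) to receive another loading dose 1 week prior to the next scheduled dose". Table 4 footnote e and the Appendix K copy of footnote i say the same.
- SAP 1.1: the patient returns "for an unscheduled visit 1 week prior to the next scheduled dose in order to receive an additional loading dose".
- Protocol synopsis: the patient "should return to the site for an unscheduled visit to receive another loading dose prior to their next scheduled visit". No interval is given, but the next scheduled visit is kept. The Appendix K body text is similar.

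Protocol 6.1.3 also states the 1-week rule, but then adds a sentence found nowhere else: "The patient should then resume subsequent dosing visits every 14 days after the loading dose".

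Two further statements matter. Protocol 2.2.3 describes the starting regimen as a "single priming dose on Day 0, followed by bi-weekly dosing on Days 7, 21, 35, 49". Protocol 4.4 places the Part A end-of-treatment visit "1 week after administration of the last dose of study drug during Part A (Week 26/Day 182").

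**The concern.** If the loading dose is given one week before the next scheduled dose, that dose is due 7 days later. Counting 14 days from the loading dose passes over it and moves every later Part A dose 7 days off the planned days. The two sentences of the note give different dates for the next infusion.

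The 7-day follow-on dose is what makes the extra infusion a loading dose: it repeats the Day 0/Day 7 start. Without it, the patient has one infusion a week late and then ordinary maintenance dosing. At stake are one dose of the intended regimen and, in the BIVV009 arm, a longer interval between active doses at the crossover, where those patients receive placebo to keep the blind. Section 6.1.3 is the visit-by-visit section for Part A, so sites are likely to consult it.

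**Working it through.** **Inputs.** Dosing days: Protocol 4.1. Planned number of Part A doses, 14, and exclusion of the Week 26 dose from Part A exposure: SAP 4.7.1. Week 26 visit on Day 182: Protocol 4.4 and 6.1.4. Placebo on Day 182 for the BIVV009 arm, and active dosing from Week 27: Protocol 4.1, Part B. Week 27 is Day 189. All doses are taken on their nominal day, and Day 182 is held fixed.

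**1. The plan's own figure.** Day 0, plus Days 7, 21, ..., 175. The second group has (175 − 7)/14 + 1 = 13 doses, so the total is 14, as SAP 4.7.1 states.

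**2. One missed dose.** Write the missed day as m = 7 + 14j with j = 0, ..., 11, which gives the 12 cases from Day 7 to Day 161. Doses already given: 1 + j. Loading dose: m + 7 = 14 + 14j. Next scheduled dose: m + 14 = 21 + 14j.

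- *1-week rule.* Loading dose, then Days 21 + 14j, ..., 175. Count: (1 + j) + 1 + (12 − j) = 14. Last dose Day 175.
- *Literal sentence.* Days 14 + 14j, 28 + 14j, ..., 168; the next 14-day slot is Day 182, which is the crossover dose. Count: (1 + j) + (12 − j) = 13. Last dose Day 168. 13/14 = 92.9%.

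The result does not depend on j, so it holds in all 12 cases.

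**3. Example, Day 91 missed.** Both readings give Days 0 to 77 (7 doses) and a loading dose on Day 98. The 1-week rule continues with Days 105, 119, 133, 147, 161, 175: 7 + 1 + 6 = 14. The literal sentence continues with Days 112, 126, 140, 154, 168: 7 + 1 + 5 = 13.

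**4. End of Part A and crossover.**

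| | 1-week rule | Literal sentence |
|---|---|---|
| Part A doses | 14 | 13 |
| Last Part A dose | Day 175 | Day 168 |
| Last dose to Week 26 visit | 182 − 175 = 7 days | 182 − 168 = 14 days |
| Last active Part A dose to Day 189, BIVV009 arm | 189 − 175 = 14 days | 189 − 168 = 21 days |

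**5. The gap caused by the miss itself.** For m from 21 to 161, the previous dose was on m − 14 and the loading dose is on m + 7, so 21 days pass under either reading. For m = 7 the gap is 14 − 0 = 14 days. The miss therefore causes a 21-day gap in 11 of 12 cases whichever reading is used, and the literal sentence adds a further one at crossover.

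**6. Outside these conditions.** Two consecutive missed doses give 12 doses (last on Day 168) on the literal reading and 13 (last on Day 175) under the 1-week rule. If Day 175 is missed, no later Part A dose exists and none of these figures applies.

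**The case against.** The strongest reply is that the sentence can be read consistently. To resume suggests going back to an existing schedule, and every 14 days is that schedule's frequency. The preceding sentence presupposes that the next scheduled dose is given. On that reading the patient takes that dose and then continues every 14 days, as the other sections imply. This is probably what was meant, and many sites would act on it. But the words count the 14 days from the loading dose, so the intended reading has to be recovered from elsewhere.

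A second reply is that the crossover gap is not a new level of exposure loss: a missed dose already produces a 21-day gap in 11 of 12 cases, and the corrected wording does not remove that gap. This stands. The literal sentence adds an avoidable second gap, longer than the 17 days that the note itself uses as a trigger for re-loading.

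A third reply is that Protocol 4.4 describes planned duration. Any missed Day 175 dose would also depart from it. That is fair; the 14 days before Week 26 are a consequence of the wording, not a separate breach.

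A reader might go further and infer that the note cannot be followed at all, because each re-anchored dose would be out of window and would trigger another loading dose. The documents do not support this. It assumes that the windows stay on the original calendar, while the sentence moves the dosing visits and nothing says that their windows do not move with them.

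**Conclusion.** The point holds as a wording conflict with a definite but narrow consequence. For exactly one missed dose from Day 7 to Day 161, a site following the last sentence of the 6.1.3 note gives one Part A dose fewer than the 1-week rule provides. It also doubles the interval from last dose to the Week 26 visit and leaves 21 days instead of 14 between active doses at crossover in the BIVV009 arm. This rests on nominal dosing days, a fixed Day 182 and a literal reading. The documents give no missed-dose rate, so no number of patients can be stated.

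Two stronger conclusions are not supported. First, loss of complement inhibition: Protocol 2.2.3 requires concentrations of at least 20 µg/mL at trough, but nothing in the documents shows that a 21-day interval falls below that. Second, damage to the primary analysis: SAP 4.1 averages whichever of the Week 23, 25 and 26 values are available, so responder status can still be derived. A haemoglobin value 14 days after a dose is also not unusual here. On the planned calendar the pre-dose values on Days 161 and 175 are each taken 14 days after the previous dose. No alpha, power or sample-size figure is affected.

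The sentence should be corrected, because the right rule is already stated elsewhere and no new design decision is needed.

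**What to change.** Replace the last sentence of the Protocol 6.1.3 note with: *The patient should then receive the next scheduled dose 7 days after the loading dose and continue every 14 days on the original calendar (through Day 175).*

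The cost is one sentence in the next protocol amendment, with the IRB/EC submission that Protocol 8.1 requires, and a short memo to sites. SAP 1.1 already carries the 1-week rule and needs no change.

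The replacement does not cover a missed Day 175 dose. One week before the next active dose on Day 189 is Day 182, the blinded crossover visit at which the BIVV009 arm receives placebo. That case would need its own instruction.
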